4.4 Secondary efficacy criteria

4.4.1 Overall Survival

4.4.1.1 Definition

It is defined as the time interval between the date of inclusion and the date of death (regardless of cause).

Patients lost to follow-up or alive at the time of analysis will be censored at the date of last news. A minimum follow-up of 1 year for the last included patient is required.

4.4.1.2 Evaluation

The time scale considered will be the month.

Overall survival will be plotted using the Kaplan Meier estimator and survival rates at different time points (3, 6, 9, 12 and 18 months) will be calculated along with their 95% confidence intervals.

4.4.2 Tumoral control (centralised review)

4.4.2.1 Definition

It is defined as the percentage of patients with a complete, partial, or stable tumor response at 2 months after the start of treatment as assessed by centralized review according to RECIST v1.1 criteria.

Patients who have stopped treatment before the 2-month assessment will be considered as having failed tumor control.

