## 6. DIAGRAM OF THE STUDY

This is a single-arm Phase II study. All patients included, after verification of the inclusion criteria, will be treated according to the same regimen. Each cycle lasts 28 days (21 days of treatment and 7 days without treatment).

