#### 2) Secondary criteria

The **secondary endpoints** are defined as follows:

- Overall treatment **tolerance** will be assessed by the rate of observed toxicities, graded according to NCI-CTC v4.

- **Overall survival is** defined as the time from the date of inclusion to the date of death from any cause. Patients lost to follow-up or alive at the time of analysis will be censored at the date of last report. A minimum follow-up of 1 year for the last included patient is required.

- **The tumor control rate** assessed in centralized review is defined as the percentage of patients with complete tumor response, partial tumor response, or tumor stability on regorafenib therapy 2 months after the start of therapy (RECIST criteria V1.1).

- **The objective response rate is** defined as the occurrence of at least one complete or partial response assessed from the best response (according to RECIST v1.1 criteria) during the treatment evaluations (Appendix 4). Patients who discontinue the study without response assessment will be considered non-responders.

- **Time to treatment failure is** defined as the time from the date of inclusion to the date of treatment discontinuation (regardless of cause) or death (regardless of cause). Living patients without treatment discontinuation will be censored at the date of last treatment administration.

- **Progression-free survival is** defined as the time from the date of inclusion to the date of first investigator-rated progression (clinical or radiological) or death (from any cause). Patients alive without progression will be censored at the date of last news. A minimum

follow-up of 1 year for the last included patient is required.

- **The regorafenib dose intensity** will be calculated during the first 2 cycles of treatment **and over the** entire treatment period. The theoretical dose intensity (TDI) (mg/cycle) is 3360 mg ((160mg/d x 21d ). The dose intensity (DI) actually received is equal to the total dose received divided by the total duration of treatment. The relative dose intensity (DIR) is equal to DI / DIT.

- **Time to deterioration in independence** is defined as the time from the date of inclusion to the date on which the IADL score (Appendix 2) has decreased by at least 1 point from the score calculated at inclusion. Patients alive or deceased without deterioration of autonomy will be censored at the date of last IADL assessment or the date of death.

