## **11.3 Calculation of the number of subjects required**

The clinical assumptions are based on data from the CORRECT study and are as follows:

$H_0$  : A tumor control rate at 2 months after the start of treatment of 25% or less is not sufficient

$H_1$  : A tumor control rate at 2 months after the start of treatment of more than 25% is considered sufficient. A rate of 47% is expected.

With a one-sided  $\alpha$  risk of 5% and 90% power, 42 patients are required.

Patients who discontinue the study prior to documented tumor progression at 2 months will be considered non-responders for the primary endpoint analysis.

The decision rules after inclusion of 42 patients are:

If 15 or fewer patients show a complete or partial response or stability, then the treatment will be considered not effective.

If 16 or more patients have a complete, partial or stable response, then the treatment is considered effective.

A recruitment of 2 patients per month is planned.

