4.3.1 Definition

The primary endpoint is to evaluate the tumor control rate. It is defined as the percentage of patients with a complete, partial or stable tumor response 2 months after the start of treatment according to the investigator's RECIST v1.1 criteria.

Patients who stopped treatment (due to radiological progression or death) before 2 months after the start of treatment will be considered as having failed tumor control. Discontinuations for other causes will be reviewed on a case-by-case basis; verify that the patient has not taken any subsequent treatment between the date of discontinuation and the date of imaging. In case of clinical progression, if no imaging is available, the patient will be considered to have failed tumor control; otherwise, review the medical record to determine the reason for the clinical progression.

If imaging at 2 months is not available but imaging before 2 months is done then:

- Patients with radiological and/or clinical progression on a previous evaluation will be considered to have failed tumor control at 2 months.
- Patients who have died (regardless of cause) before 2 months will be considered to have failed tumor control.

If 2-month imaging is not available, subsequent imaging will be reviewed if available and the patient record will be reviewed.

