4.5.1 Regorafnib

4.5.1.1 Treatment duration

Treatment duration will be described by:

- The number of cycles per patient;
- The duration of treatment (converted into months) will be calculated by the formula
$$\text{Date last tablet taken} - \text{date first tablet taken} + 1d$$
- The therapeutic breaks and the days without taking tablets during this period will not be subtracted from this duration.

It will be described according to the usual descriptive statistics.

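### Central review fails every patient who stopped treatment early, while the investigator rate does not, so the gap between the two tumour-control rates mixes a rule difference with reader differences

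*SAP*

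**What the plan says.** - **Protocol 11.1, central endpoint.** The rate "assessed in centralized review is defined as the percentage of patients with complete tumor response, partial tumor response, or tumor stability", and the sentence goes on to require that this control be under regorafenib, 2 months after the start. The primary endpoint in the same section carries the same on-treatment condition, with the investigator as reader. Neither definition says how to count a patient who has stopped.
- **SAP 4.4.2.1, central endpoint.** Control is judged "as assessed by centralized review according to RECIST v1.1 criteria". The SAP then adds: "Patients who have stopped treatment before the 2-month assessment will be considered as having failed tumor control".
- **SAP 4.3.1, investigator endpoint.** The rule for automatic failure of tumour control reads, short of its last word: "Patients who stopped treatment (due to radiological progression or death) before 2 months after the start of treatment will be considered as having failed tumor". The rest are handled separately: "Discontinuations for other causes will be reviewed on a case-by-case basis", with a check that no later treatment was taken before the imaging. Clinical progression with no imaging also counts as failure.
- **Protocol 11.3, repeated in SAP 1.4.** "Patients who discontinue the study prior to documented tumor progression at 2 months will be considered non-responders for the primary endpoint analysis".
- **Imaging.** Scans are 8-weekly (Protocol 8.1). After a stop for a reason other than progression they continue until progression; after a stop for progression only survival and later treatments are collected (Protocol 8.2). Images go to an independent panel (Protocol 9 and 13.3).
- **Timing.** "Each cycle lasts 28 days (21 days of treatment and 7 days without treatment" (Protocol 6). SAP 4.5.1.1 measures exposure up to "Date last tablet taken". No section dates the stop for the tumour-control endpoints.
- **Analysis.** SAP 4.4.2.2 plans description and an exact one-sided 95% confidence interval for the central rate, with no threshold.

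**The concern.** The trial is open-label and single-arm, and its primary endpoint is read by the investigator. The central reading is the only independent check on it. Anyone who sees the two rates together will take a lower central rate as a sign that investigators were generous in calling control.

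That inference needs both rates to treat the same patient in the same way except for who reads the scan. Here they do not. A patient who stops for toxicity or refusal, is scanned at 8 weeks and is stable can be credited in one rate and is failed in the other before the panel's reading is considered. Protocol 8.2 keeps scanning such patients, so a readable image should normally exist. Part of any gap then comes from the rule and cannot be separated from reader disagreement.

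The undated stop adds to this. Depending on how it is coded, the central rule reaches either a small group or also the patients who stopped because of the week-8 scan.

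**Working it through.** **1. The plan's own figure.** Protocol 11.3 takes 25% against 47%, one-sided 5%, 90% power, 42 patients, effective if 16 or more are controlled. The exact binomial with 16/42 gives a one-sided type I error of 0.0416 and power of 0.906, and 42 is the smallest number that meets both limits. The figure reproduces. The expected count is 0.47 × 42 = 19.7, taken as 20 below.

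**2. The same patient under each rule.**

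| Patient | Investigator rate (SAP 4.3.1) | Central rate (SAP 4.4.2.1) |
|---|---|---|
| Stopped early for radiological progression, or died | failure | failure |
| Stopped early for another reason, stable on the 2-month scan, no new treatment | individual review, can be controlled | failure whatever the panel reads |
| On treatment at the 2-month scan | investigator's reading | panel's reading |

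The rules part only in the second row.

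**3. Effect on the central rate.** Let k be the number of second-row patients among 20 who would be controlled on their scan. The central rate is (20 − k)/42, a loss of 1/42 = 2.4 points each. The documents do not give k, so it is an assumption.

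| k | Central rate | Exact one-sided 95% lower bound |
|---|---|---|
| 0 | 20/42 = 47.6% | 34.2% |
| 1 | 19/42 = 45.2% | 32.0% |
| 2 | 18/42 = 42.9% | 29.8% |
| 3 | 17/42 = 40.5% | 27.7% |
| 4 | 16/42 = 38.1% | 25.6% |

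**4. Effect on the gap.** On a common denominator of 42, let U be the on-treatment patients whom the panel upgrades to control, D those it downgrades, and k the early stoppers credited by the investigator rule. Then

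central − investigator = (U − D − k)/42.

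- U = D = 0 and k = 2: the gap is −2/42 = −4.8 points although the readers agree on every scan.
- U = 2, D = 0 and k = 2: the gap is 0 although they disagree on two.

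The rule contributes −k/42. It does not fix the sign of the whole gap.

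**5. The stop date.** The last planned tablet of cycle 2 falls on day 28 + 21 = 49. The scan is due at about day 8 × 7 = 56.

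- Coded on the last tablet, a patient who stops because of the week-8 scan stopped before it. That patient fails centrally without the panel's reading being used.
- Coded on the decision to stop, the same patient was still on treatment at the assessment, and the panel's reading counts.

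The two SAP sections also use different anchors: 4.3.1 counts from 2 months after the start, which at the SAP's 30.4375 days per month is day 60.9, and 4.4.2.1 counts from the assessment itself.

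**The case against.** The strongest reply is that SAP 4.4.2.1 is the rule closer to the protocol. Protocol 11.1 asks for control under regorafenib, and Protocol 11.3 makes those who leave the study before documented progression non-responders for the primary endpoint. Failing patients who are off drug is then a conservative composite, and the individual review in SAP 4.3.1 is the looser rule. This stands to a large extent. It means that a downward bias cannot be asserted without naming the target: the central rate is lower relative to SAP 4.3.1 or to a purely scan-based reading, not plainly relative to the protocol. It does not explain why one on-treatment condition is applied in two ways.

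A reader might also infer more than the text supports:

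- **That the panel can take control away but never restore it.** This is true only of early stoppers. On the plain reading, a patient stopped because of the week-8 scan did not stop before it, and the panel may read stability.
- **That the last tablet is the stop date.** SAP 4.5.1.1 is an exposure formula in the safety section. SAP 4.4.4.1 names the date of discontinuation and the date of last administration as separate things, and the off-week belongs to the cycle. Last-tablet coding is a possibility left open, not the rule.
- **That patients stopped on an early scan called progressive are a large further loss.** Such scans fall outside the 8-weekly schedule, and Protocol 8.2 plans none after a stop for progression, so these patients would usually have no 2-month image under any rule.
- **That the central rate could miss the 16/42 threshold.** That threshold belongs to the primary endpoint.

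Finally, neither document plans a formal comparison of the two readings. That limits the consequence, but the two rates will still be reported for the same trial and compared.

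**Conclusion.** The concern holds in a limited form. The two tumour-control rates handle early stops for reasons other than progression or death differently, so the difference between them is not a clean measure of reader disagreement. The size is 2.4 points per affected patient: 4.8 points for two and 9.5 for four (4/42). This assumes a denominator of 42, about 20 patients controlled on scan, and affected patients whom the individual review in SAP 4.3.1 would credit.

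The missing stop date is a second, real gap. How much it matters depends on the coding convention, which the documents leave open.

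The documents do not support saying that the central rate is biased downward in general or that the panel is unable to reverse investigators' calls. The trial's decision on efficacy is unaffected, because the endpoint is secondary and only described.

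**What to change.** Before the database freeze, which SAP 1.6 sets as the limit for changes:

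1. Put one identical early-stop rule, with one time anchor, in SAP 4.3.1 and 4.4.2.1.
2. State that a stop before the 2-month assessment is dated by the decision to discontinue, so that neither the planned off-week nor a stop prompted by the 2-month scan counts as one.
3. For stops for reasons other than progression, where imaging exists before any new anti-cancer treatment, classify the patient in the same way for both readings.
4. Report the central rate with all early stoppers as failures as a sensitivity analysis, to respect the protocol's on-treatment condition.
5. Tabulate investigator against central reading in the same patients. The population needs settling for this: the table in SAP section 4 puts both endpoints on ITT, while SAP 4.3 and 4.3.2 put the primary endpoint on the modified ITT population.

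The cost is SAP wording, one sensitivity analysis and one extra table. The plan already provides for collecting the scans and reading them centrally.

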4.4.2.2 Evaluation

This criterion will be described according to the usual descriptive statistics. A one-sided 95% confidence interval will be calculated using the exact method.

4.4.3 Objective response

4.4.3.1 Definition

It is defined as the percentage of patients in objective response, i.e., complete response (CR) or partial response (PR) as assessed by the investigator according to RECIST v1.1 criteria. The objective response will be determined from the best response during treatment assessments. Patients who discontinue treatment without response assessment will be considered as having no objective response.

4.4.3.2 Evaluation

Objective tumor response rates will be described according to standard descriptive statistics.

4.4.4 Time to therapeutic failure

4.4.4.1 Definition

It is defined as the time between the date of inclusion and the date of treatment discontinuation (regardless of cause).

Living patients without treatment discontinuation will be censored at the date of last treatment administration.

4.4.4.2 Evaluation

The time scale considered will be months.

The time to treatment failure will be plotted using the Kaplan Meier estimator and the rates at 6, 9, 12, 18 months will be calculated along with their 95% confidence intervals.

4.4.5 Progression-Free Survival

4.4.5.1 Definition

Elle est définie comme l'intervalle de temps entre la date d'inclusion et la date de 1^{ère} progression radiologique et/ou clinique selon l'investigateur ou la date de décès (quelle qu'en soit la cause). Les patients vivants et sans progression seront censurés à la date de dernières nouvelles. Un minimum d'un an pour le dernier patient inclus est nécessaire.

4.4.5.2 Evaluation de la survie sans progression

L'échelle de temps considérée sera le mois.

La survie sans progression sera représentée graphiquement grâce à l'estimateur de Kaplan Meier et les taux de survie à différentes temporalités (6, 9, 12 et 18 mois) seront calculés ainsi que leurs intervalles de confiance à 95 %.

4.4.6 Time to autonomy deterioration

The analysis will be done if we have the questionnaire at baseline and at least one follow-up for the majority of patients.

4.4.6.1 Definition

It is defined as the time between the date of inclusion and the date on which the IADL score decreased by at least one point from the score at inclusion. Patients alive or deceased without deterioration of autonomy will be censored at the date of last IADL assessment or the date of death.

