## **11.2 Exploratory evaluation of geriatric parameters**

It is recommended that each patient has had a geriatric consultation prior to inclusion.

An exploratory analysis is planned to look for geriatric prognostic factors for the primary endpoint. An analysis of the evolution of geriatric parameters during the follow-up will also be performed.

The "patient" self-questionnaire including the collection of activity of daily living and the "team" questionnaire including the quality of life (Spitzer QoL Index) will be completed at inclusion and at each evaluation (every 4 weeks).

The self-questionnaire will be completed by the patient. The "team" questionnaire will be completed by a clinical research associate, a nurse or the investigator depending on the organization of the service.

The 2 questionnaires include the assessment of geriatric parameters with the following domains: functional status, mobility, cognition, depression, energy, social context and quality of life; physical activity, nutrition, hearing and vision will only be completed at inclusion. A cut-off value is determined for each domain.

The questionnaires and self-questionnaires are presented in Appendices 2 and 3. These evaluation questionnaires have been used in onco-geriatrics, particularly as self-questionnaires (10-14).

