### **b) Instrumental activities of daily living (IADL) (Self questionnaire)**

The self-administered questionnaire reproducing the IADL items will be used to measure instrumental activities of daily living (IADL) (17). Disability in an IADL is defined as the need for assistance to complete at least one IADL. The denominator will be adjusted to account for patients not performing certain activities listed in the IADL.

The threshold value is: <14 when the patient does or did all IADL activities. A score lower than 14/14 is considered pathological (e.g., if the patient needs help with housework and managing money, the score will be 12/14 and therefore pathological). If the patient has never done certain activities, the score is adjusted according to the denominator corresponding to the maximum number of points possible on the activities performed by the patient (e.g.: if the patient has never done housework, the score will be 12/12, and the IADL is considered normal).

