4.4.6.2 Evaluation

The time scale considered will be the month.

The time to degradation of autonomy will be plotted using the Kaplan Meier estimator and the 6, 9, 12, 18 month rates will be calculated along with their 95% confidence intervals.

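### One unconfirmed 1-point IADL fall counts as permanent loss of autonomy, and no analysis separates lasting falls from transient falls or reporting error

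*SAP*

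**What the plan says.** Time to loss of autonomy is a secondary objective in both documents. SAP 4.4.6.1 runs the time from inclusion to "the date on which the IADL score decreased by at least one point from the score at inclusion". Protocol section 11.1 agrees: the score "has decreased by at least 1 point from the score calculated at inclusion". Patients without such a fall are censored at their last IADL assessment or at death. Neither document asks for a second questionnaire to confirm the fall, says what happens if the score recovers, or gives a test-retest or minimal-change figure.

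Protocol section 11.2, item 2) b), describes the scale: "The threshold value is: <14 when the patient does or did all IADL activities". Its examples show the scoring: "if the patient needs help with housework and managing money, the score will be 12/14 and therefore pathological", and "if the patient has never done housework, the score will be 12/12". The patient completes the form at inclusion and every 4 weeks (protocol 11.2), but only until progression (protocol 8.1).

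SAP 4.4.6.2 then tabulates the Kaplan-Meier curve: "the 6, 9, 12, 18 month rates will be calculated along with their 95% confidence intervals".

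**The concern.** The event is the smallest fall the scale appears able to register, seen once, on a form the patient fills in. If the next form is back at the inclusion score, the event stands. For a patient who enters at the maximum, an answering error can only lower the score and so can only create an event. Each further questionnaire gives another chance, so false events accumulate over time.

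The study sets out to describe the effect of regorafenib on elderly patients, including geriatric parameters. With one arm, no control curve shows how much of the apparent loss of autonomy is transient or is reporting error. A reader of the 6-month rate could take it as lasting loss when part of it is not.

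**Working it through.** The plan gives no expected rate or noise level for this endpoint, so there is no planned figure to reproduce. The check asks what the planned rule would report if nothing changed.

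**Inputs from the documents**
- Scale: help with two activities costs 2 points, and leaving out one activity lowers the maximum by 2. This implies 14 / 2 = 7 items scored 0 to 2, with a smallest step of 1. It is inferred from the examples, because the questionnaire itself (Appendix 2) is not in the available text.
- Six follow-up questionnaires by week 24 (24 / 4 = 6).
- Time under assessment: no figure is given. The proxy is the median treatment duration in the cited phase III study, 7.6 weeks under 65 years and 7.1 weeks over 65 (protocol 1.2). The calculation uses 7.6.

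**Assumptions**
- True status stays at 14/14.
- Each item is misreported one step down, independently, with probability e = 0.25% to 3%, at inclusion and at every follow-up.
- Assessment stops exponentially.

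**Step 1: false fall on one form.** With a correct inclusion score, q = 1 − (1 − e)^7. At e = 1%, q = 1 − 0.99^7 = 6.8%.

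**Step 2: first-fall rate over six forms.** With a correct inclusion score the rate is 1 − (1 − q)^6 = 1 − 0.9321^6 = 34.4%. If b points were lost by error at inclusion, a false fall needs more than b errors. Averaging over b at e = 1%: 0.932 × 0.344 + 0.066 × 0.012 = 32%. Stopping unrelated to the noise leaves the expected Kaplan-Meier rate essentially unchanged.

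**Step 3: early stopping.** The chance of still being assessed 4 weeks later is s = exp(−ln 2 × 4 / 7.6) = 0.694. The share reaching six forms is s^6 = 11%, or about 4.7 of 42 patients. The share with no follow-up form is 1 − s = 31%. The crude share with a false event is q·s / (1 − (1 − q)·s), averaged over b. At e = 1%: 0.932 × 0.134 + 0.066 × 0.0045 = 12%.

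**Step 4: definitive rule.** The event is a fall not followed by any later form at or above the inclusion score, and a fall on the last form counts. A false fall then survives mainly when it is on the last form. At e = 1% that is roughly 0.068 × 0.306 = 2.1% per form, so 1 − 0.979^6 = 12% over six forms. Simulation, which includes error in the inclusion score, gives 11%.

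| Item error e | False fall per form q | 6-month KM, first fall | Crude share, first fall | 6-month KM, definitive (simulated) |
|---|---|---|---|---|
| 0.25% | 1.7% | 10% | 4% | 3% |
| 0.5% | 3.4% | 18% | 7% | 6% |
| 1% | 6.8% | 32% | 12% | 11% |
| 2% | 13.2% | 50% | 20% | 19% |
| 3% | 19.2% | 60% | 25% | 25–26% |

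**Sensitivity**
- If 15% of items already need help at entry, the six-form first-fall rates at 1%, 2% and 3% are 31%, 48% and 58%, so the ceiling assumption matters little.
- With all six forms completed by everyone, the definitive rates would be 6%, 12% and 16%. If no forms after week 24 were available under early stopping, they would be about 15%, 25% and 33%, because every fall on the sixth form would count as a last-form fall.
- The crude share under the definitive rule with early stopping is about 4%, 8% and 11%.
- Under pure noise, the form before a last-form fall is itself a fall only with probability q. So at least 1 − q of the definitive events rest on a single last form: about 93%, 87% and 81% at 1%, 2% and 3%.

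**The case against.** A reader might infer that reporting error by itself produces a large 6-month deterioration rate. The documents do not support that as a fact. They give no reliability figure, and the size follows entirely from the assumed error. If the chance of a false fall were 1% per whole form rather than per item, the six-form rate would be 1 − 0.99^6 = 5.9%. The share of patients entering at 14/14 is also unknown: eligibility requires ECOG 0 or 1, but no IADL distribution is given.

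A reader might also infer that six-questionnaire rates describe the share of patients affected, or that a persistence rule brings them down to 6% to 16%. Both would need everyone to complete six forms, whereas assessment ends at progression. The crude share of false events is much smaller than the Kaplan-Meier rate, and about 5 of 42 patients at week 24 would give a visibly wide confidence interval. The Kaplan-Meier rate is still the figure the SAP tabulates, and its expected inflation remains.

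The 1-point threshold fits the protocol's own view that any score below the patient's maximum is abnormal. That cut-off classifies status at one time, however. It does not show that a change between two self-reports is real or lasting. Whether to study first or definitive deterioration is a legitimate choice of estimand, so nothing here justifies displacing the protocol-defined endpoint.

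Both documents also plan repeated-measures mixed models of IADL. These describe the average course, including recovery, and soften the problem, but they do not correct the time-to-event rate.

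Finally, the endpoint is one of ten secondary objectives. It has no test or decision rule, and SAP 4.4.6 makes it conditional on enough questionnaires. That limits how much is at stake.

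**Conclusion.** The concern holds as a gap in the definition. One unconfirmed minimum-step fall is a permanent event, repeated assessment lets false and transient falls accumulate, and nothing planned shows how many of the events last. With independent item error of 0.25% to 3% and no true change from 14/14, the 6-month Kaplan-Meier rate would be about 10% to 60%. With stopping at a 7.6-week median, the crude share of patients with a false event would be about 4% to 25%. These figures rest on the assumed error, on independence between forms, on the inferred 7-item scoring and on treatment duration standing in for time under assessment. They show that the rate is sensitive to noise; they do not predict what the trial will find. The primary endpoint and its decision rule are not touched.

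**What to change.** Keep the first-fall analysis in SAP 4.4.6 as the protocol-defined endpoint and add a definitive-deterioration sensitivity analysis:
- **Event:** the first questionnaire with a fall of at least 1 point from the inclusion score that is not followed by any later questionnaire at or above the inclusion score. A fall on the last available questionnaire counts.
- **Reporting:** show both curves, and give the number of definitive events that rest on a last, unconfirmed questionnaire.
- **Wording:** describe loss of autonomy as lasting only where the definitive curve supports it.

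The cost is one SAP paragraph and one more Kaplan-Meier curve from questionnaires already collected. SAP 1.6 allows such changes before the database is frozen.

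The downsides are fewer events and residual noise. With early stopping the noise-only 6-month rate falls to about 3% to 26%, not to zero. What remains comes from last-questionnaire falls and from error in the inclusion score, which every later comparison shares.

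The same sensitivity analysis for the Spitzer endpoint (SAP 4.4.7) is optional. That endpoint already needs a 2-point change, and the effect there was not quantified.
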